5. POSSIBLE RISKS AND ANALYSIS OF RISK/BENEFIT RATIO

Only subjects who have been selected as a surgical candidate for sensory nerve decompression of chronic headache would have their tissue tested. The taking of the periosteal sample would add no additional risk to the operation, as we are obtaining tissue *discarded* during surgery.

Botox therapy is currently approved by the FDA for preventive treatment of migraines.

All the potential risks of Botox injections as issued by the FDA are as follows. As we are only injecting the back of the occiput, symptoms occurring around the eyes, the oropharynx or generalized symptoms are very unlikely.

A. General:

- There have been rare spontaneous reports of death, sometimes associated with dysphagia, pneumonia, and/or other significant debility, after treatment with botulinum toxin.
- *There have also been rare reports of adverse events involving the cardiovascular system, including arrhythmia and myocardial infarction, some with fatal outcomes. Some of these patients had risk factors including cardiovascular disease. The exact relationship of these events to the botulinum toxin injection has not been established.*

- The following events have been reported since the drug has been marketed and a causal relationship to the botulinum toxin injected is unknown: skin rash (including erythema multiforme, urticaria and psoriasisiform eruption), pruritus, and allergic reaction.
- In general, adverse events occur within the first week following injection of **BOTOX®** and while generally transient may have a duration of several months. Localized pain, tenderness and/or bruising may be associated with the injection. Local weakness of the injected muscle(s) represents the expected pharmacological action of botulinum toxin. However, weakness of adjacent muscles may also occur due to spread of toxin.
- Extraocular muscles adjacent to the injection site can be affected, causing ptosis or vertical deviation, especially with higher doses of **BOTOX**. The incidence rates of these adverse effects in 2058 adults who received a total of 3650 injections for horizontal strabismus are 15.7% and 16.9%, respectively.
- The incidence of ptosis was 0.9% after inferior rectus injection and 37.7% after superior rectus injection.

B. Side effects and discomforts associated with study treatment that you may experience include the following and some of these effects may last as long as 3 to 4 months:

- Drooping of the upper lid

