Rizatriptan (Maxalt® tablets) / Zolmitriptan (Zomig® tablets) / Frovatriptan (Frova® tablets)				
Fiorinal® / Fioricet® / Esgic				
Dihydroergotamine mesylate (Migranal® nasal spray)				
Metoclopramide (Reglan®)				
Other treatment to stop headache:				
Acupuncture / Acupressure				
Physical therapy				
Stress reduction				
Ice / cold compresses				
Riboflavin (vitamin B-2) / Magnesium / Herbs (feverfew, etc.)				
Prednisone				
Oxygen				
Yoga / Meditation				
Massage Therapy				
Chiropractic Therapy				
Biofeedback				
Nerve blocks				
Botulinum toxin (Botox®)				
Other: _____				

Are you allergic to any medications? Yes No

If Yes, please list: _____

What are your specific goals for treatment? (What do you hope to get out of your treatment here?)

X _____ or **X** _____ and _____
Patient's Signature Person authorized to sign for patient Relationship to patient

Date: ____ / ____ / ____ Time: ____ : ____ a.m.
 p.m.

Please bring any previous records / CT scan / MRI / X-rays to your visit if possible.

Thank you for taking the time to fill out this form before your visit.

X _____ M.D. _____ M.D. _____ / _____ / _____
Signature Print Name Date Time (24 hour)

HIGHLIGHTS OF PRESCRIBING INFORMATION

These highlights do not include all the information needed to use BOTOX® safely and effectively. See full prescribing information for BOTOX.

BOTOX (onabotulinumtoxinA) for injection, for intramuscular, intradetrusor, or intradermal use

Initial U.S. Approval: 1989

WARNING: DISTANT SPREAD OF TOXIN EFFECT

See full prescribing information for complete boxed warning.

The effects of BOTOX and all botulinum toxin products may spread from the area of injection to produce symptoms consistent with botulinum toxin effects. These symptoms have been reported hours to weeks after injection. Swallowing and breathing difficulties can be life threatening and there have been reports of death. The risk of symptoms is probably greatest in children treated for spasticity but symptoms can also occur in adults, particularly in those patients who have an underlying condition that would predispose them to these symptoms. (5.2)

RECENT MAJOR CHANGES

- Warnings and Precautions (5.5, 5.7, 5.13, 5.14) 4/2017

INDICATIONS AND USAGE

BOTOX is an acetylcholine release inhibitor and a neuromuscular blocking agent indicated for:

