- Cervical Dystonia: Base dosing on the patient's head and neck position, localization of pain, muscle hypertrophy, patient response,

and adverse event history; use lower initial dose in botulinum toxin naïve patients (2.6)

- Axillary Hyperhidrosis: 50 Units per axilla (2.7)
- Blepharospasm: 1.25 Units-2.5 Units into each of 3 sites per affected eye (2.8)
- Strabismus: The dose is based on prism diopter correction or previous response to treatment with BOTOX (2.9)

DOSAGE FORMS AND STRENGTHS

Single-use, sterile 100 Units or 200 Units vacuum-dried powder for reconstitution only with sterile, preservative-free 0.9% Sodium Chloride Injection USP prior to injection (3)

CONTRAINDICATIONS

- Hypersensitivity to any botulinum toxin preparation or to any of the components in the formulation (4.1, 5.4, 6)
- Infection at the proposed injection site (4.2)
- Intradetrusor Injections: Urinary Tract Infection or Urinary Retention (4.3)

WARNINGS AND PRECAUTIONS

- Potency Units of BOTOX are not interchangeable with other preparations of botulinum toxin products (5.1, 11)
- Spread of toxin effects; swallowing and breathing difficulties can lead to death. Seek immediate medical attention if respiratory, speech or swallowing difficulties occur (5.2, 5.6)
- Potential serious adverse reactions after BOTOX injections for unapproved uses (5.3)
- Concomitant neuromuscular disorder may exacerbate clinical effects of treatment (5.5)
- Use with caution in patients with compromised respiratory function (5.6, 5.7, 5.10)
- Corneal exposure and ulceration due to reduced blinking may occur with BOTOX treatment of blepharospasm (5.8)
- Retrobulbar hemorrhages and compromised retinal circulation may occur with BOTOX treatment of strabismus (5.9)
- Bronchitis and upper respiratory tract infections in patients treated for spasticity (5.10)
- Urinary tract infections in patients treated for OAB (5.12)
- Urinary retention: Post-void residual urine volume should be monitored in patients treated for OAB or detrusor overactivity associated with a neurologic condition who do not catheterize routinely, particularly patients with multiple sclerosis or diabetes mellitus. (5.13)

ADVERSE REACTIONS

The most common adverse reactions ($\geq 5\%$ and $>$ placebo) are (6.1):

- OAB: urinary tract infection, dysuria, urinary retention
- Detrusor Overactivity associated with a neurologic condition: urinary tract infection, urinary retention
- Chronic Migraine: neck pain, headache

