Table 14 presents the most frequently reported adverse reactions in a placebo-controlled, double-blind post-approval 52 week study with BOTOX 100 Units (Study NDO-3) conducted in MS patients with urinary incontinence due to detrusor overactivity associated with a neurologic condition. These patients were not adequately managed with at least one anticholinergic agent and not catheterized at baseline. The table below presents the most frequently reported adverse reactions within 12 weeks of injection.

Table 14: Adverse Reactions Reported by $> 2\%$ of BOTOX treated Patients and More Frequent than in Placebo-treated Patients Within the First 12 Weeks after Intradetrusor Injection (NDO-3)

Adverse Reactions	BOTOX 100 Unit (N=66)	Placebo (N=78)
Urinary tract infection	17 (26%)	5 (6%)
Bacteriuria	6 (9%)	4 (5%)
Urinary retention	10 (15%)	1 (1%)
Dysuria	3 (5%)	1 (1%)
Residual urine volume*	11 (17%)	1 (1%)

* Elevated PVR not requiring catheterization. Catheterization was required for PVR ≥ 350 mL regardless of symptoms, and for PVR ≥ 200 mL to < 350 mL with symptoms (e.g., voiding difficulty).

The following adverse events with BOTOX 100 Units were reported at any time following initial injection and prior to re-injection or study exit (median duration of exposure was 51 weeks): urinary tract infections (39%), bacteriuria (18%), urinary retention (17%), residual urine volume* (17%), dysuria (9%), and hematuria (5%).

No difference in the MS exacerbation annualized rate (i.e., number of MS exacerbating events per patient-year) was observed (BOTOX =0, placebo =0.07).

Chronic Migraine

In double-blind, placebo-controlled chronic migraine efficacy trials (Study 1 and Study 2), the discontinuation rate was 12% in the BOTOX treated group and 10% in the placebo-treated group. Discontinuations due to an adverse event were 4% in the BOTOX group and 1% in the placebo group. The most frequent adverse events leading to discontinuation in the BOTOX group were neck pain, headache, worsening migraine, muscular weakness and eyelid ptosis.

The most frequently reported adverse reactions following injection of BOTOX for chronic migraine appear in Table 15.

Table 15: Adverse Reactions Reported by $\geq 2\%$ of BOTOX treated Patients and More Frequent than in Placebo-treated Patients in Two Chronic Migraine Double-blind, Placebo-controlled Clinical Trials

Adverse Reactions by System Organ Class	BOTOX 155 Units-195 Units (N=687)	Placebo (N=692)
Nervous system disorders		

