Headache	32 (5%)	22 (3%)
Migraine	26 (4%)	18 (3%)
Facial paresis	15 (2%)	0 (0%)
Eye disorders		
Eyelid ptosis	25 (4%)	2 (<1%)
Infections and Infestations		
Bronchitis	17 (3%)	11 (2%)
Musculoskeletal and connective tissue disorders		
Neck pain	60 (9%)	19 (3%)
Musculoskeletal stiffness	25 (4%)	6 (1%)
Muscular weakness	24 (4%)	2 (<1%)
Myalgia	21 (3%)	6 (1%)
Musculoskeletal pain	18 (3%)	10 (1%)
Muscle spasms	13 (2%)	6 (1%)
General disorders and administration site conditions		
Injection site pain	23 (3%)	14 (2%)
Vascular Disorders		
Hypertension	11 (2%)	7 (1%)

Other adverse reactions that occurred more frequently in the BOTOX group compared to the placebo group at a frequency less than 1% and potentially BOTOX related include: vertigo, dry eye, eyelid edema, dysphagia, eye infection, and jaw pain. Severe worsening of migraine requiring hospitalization occurred in approximately 1% of BOTOX treated patients in Study 1 and Study 2, usually within the first week after treatment, compared to 0.3% of placebo-treated patients.

Upper Limb Spasticity

The most frequently reported adverse reactions following injection of BOTOX for adult upper limb spasticity appear in Table 16.

Table 16: Adverse Reactions Reported by $\geq 2\%$ of BOTOX treated Patients and More Frequent than in Placebo-treated Patients in Adult Upper Limb Spasticity Double-blind, Placebo-controlled Clinical Trials

Adverse Reactions by System Organ Class	BOTOX 251 Units-360 Units (N=115)	BOTOX 150 Units-250 Units (N=188)	BOTOX <150 Units (N=54)	Placebo (N=182)
Gastrointestinal disorder				
Nausea	3 (3%)	3 (2%)	1 (2%)	1 (1%)
General disorders and administration site conditions				
Fatigue	4 (3%)	4 (2%)	1 (2%)	0
Infections and infestations				
Bronchitis	4 (3%)	4 (2%)	0	2 (1%)
Musculoskeletal and connective tissue disorders				
Pain in extremity	7 (6%)	10 (5%)	5 (9%)	8 (4%)
Muscular weakness	0	7 (4%)	1 (2%)	2 (1%)

Twenty two adult patients, enrolled in double-blind placebo controlled studies, received 400 Units or higher of BOTOX for treatment of upper limb spasticity. In addition, 44 adults received 400 Units of BOTOX or higher for four consecutive treatments over approximately one year for treatment of upper limb spasticity. The type and frequency of adverse reactions observed in patients treated with 400 Units of BOTOX were similar to those reported in patients treated for upper limb spasticity with 360 Units of BOTOX.

Lower Limb Spasticity

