All proposed procedures are part of standard care for chronic migraine patients except for unilateral injection of Botox for which the risks are explained above.

Describe explicitly the methods for ensuring the safety of subjects. Provide objective criteria for removing a subject from the study, for example, objective criteria for worsening disease/lack of improvement and/or unacceptable adverse events. The inclusion of objective drop criteria is especially important in studies designed with placebo control groups.

From the time of informed consent and for 3 months following injection, all self-reported adverse events will be reviewed by the study physician at each patient contact (patients are followed every 4 weeks after botox injection and one week, one month, three months, one year and after that yearly after surgery). All serious adverse events will be reported to the IRB and designated

safety monitor within 24 hours of awareness of the event. All unanticipated problems involving risks to subjects or others including adverse events will be presorted to the PHRC in accordance with PHRC unanticipated problems including adverse events reporting guidelines.

Patients will not be included in the study if they are deemed poor candidates for surgery (screening occurs independent of this study).

Only subjects who have been selected as a surgical candidate for sensory nerve decompression of chronic headache would have their tissue tested. The taking of the periosteal sample would add no additional risk to the operation, as we are obtaining tissue discarded during surgery.

Botox therapy is currently approved by the FDA for preventive treatment of migraines. Possible side effects of Botox therapy include bruising, pain during injection, twitching, itching, and numbness.

Overall, we believe the risks of this study are sufficiently low and that the benefits of information to be gained and the potential benefit of improved migraine treatment outweigh the risks in this study.

Patients can elect to withdraw from the study at any time.

FORESEEABLE RISKS AND DISCOMFORTS

Provide a brief description of any foreseeable risks and discomforts to subjects. Include those related to drugs/devices/procedures being studied and/or administered/Performed solely for research purposes. In addition, include psychosocial risks, and risks related to privacy and confidentiality. When applicable, describe risks to a developing fetus or nursing infant.

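### The risk section says it lists all FDA-issued Botox risks, but the appended label names neck pain, headache, hospital-level migraine worsening and breathing difficulty, which the list omits

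*Combined protocol and SAP*

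**What the plan says.** Protocol section 5 (Possible Risks and Analysis of Risk/Benefit Ratio) opens its list with "All the potential risks of Botox injections as issued by the FDA are as follows". The PHRC protocol summary, under Foreseeable Risks and Discomforts, uses the same sentence and essentially the same list. Both places discount symptoms around the eyes, in the oropharynx or of a generalized kind because injection is confined to the occiput. Both conclude that the study's risks are sufficiently low.

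The full prescribing information and Medication Guide are appended to the protocol. On the study's own indication they say:

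- Highlights, most common reactions (at least 5% and above placebo): "Chronic Migraine: neck pain, headache".
- Section 6.1, Chronic Migraine: "Severe worsening of migraine requiring hospitalization occurred in approximately 1% of BOTOX treated patients", against 0.3% on placebo.
- Boxed warning: "Swallowing and breathing difficulties can be life threatening and there have been reports of death".

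The safety-methods part of the PHRC summary also has a short list: "Possible side effects of Botox therapy include bruising, pain during injection, twitching, itching, and numbness".

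**The concern.** A list that claims to be complete is contradicted by its own source document, and on the indication under study. The items it lacks are the ones most relevant to injecting the neck of a patient with migraine. It does give ptosis and vertical-deviation rates from strabismus treatment, in muscles this study does not inject.

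The list matters because the low-risk conclusion follows directly from it. In the label's chronic-migraine trials, neck pain, headache and worsening migraine were among the most frequent adverse events leading to discontinuation.

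Two features of the plan add weight. The headache diary covers the three months before injection and stops there. Adverse-event review after injection covers what subjects report themselves. No planned instrument therefore asks about headache or neck pain after injection.

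**Working it through.** **Step 1. Reproduce the label's figures.** Label section 6.1, Table 15, has 687 subjects on Botox (155 to 195 Units) and 692 on placebo.

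- Neck pain: 60/687 = 8.7% (label: 9%) against 19/692 = 2.7% (label: 3%). Difference: 8.73 − 2.75 = 6.0 percentage points. Ratio: about 3.2.
- Headache: 32/687 = 4.7% (label: 5%) against 22/692 = 3.2% (label: 3%).
- Neck pain has the largest count of the 13 rows and headache is second, which agrees with the Highlights.

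**Step 2. Set the risk lists beside the label.** The lists in section 5 and in the PHRC summary are compared with the chronic-migraine and boxed-warning content.

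| Label item | Named in the risk lists? | Nearest text in the protocol |
|---|---|---|
| Neck pain | No | Localized pain tied to the injection; slight weakness of other neck muscles |
| Headache | No | None |
| Severe migraine worsening requiring hospital admission | No | Section 3.A gives continued pain on either side as a risk of one-sided injection |
| Breathing difficulty (boxed warning; label section 5.6) | No | Deaths with dysphagia or pneumonia |
| Swallowing difficulty (boxed warning) | Yes | Listed |
| Generalized weakness, double vision, drooping lid | Yes | Listed |
| Spread of toxin effect | In part | Adjacent muscles only |

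Localized injection pain does not stand in for neck pain, because Table 15 has injection-site pain as a separate row (23/687, 3%). Continued pain is neither worsening nor admission.

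**Step 3. Check the premise about the injection site.**

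- Section 3.A: occipitalis 2 × 5 = 10 Units; cervical paraspinal 4 × 5 = 20; trapezius 2 × 5 = 10. Total 40 Units, of which 30 are in neck and trapezius.
- Section 10: occipital 10 Units; trapezius 2 × 10 = 20; semispinalis 10; splenius capitis 10. Total 50 Units, of which 40 are in neck and trapezius.

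The two schemes disagree with each other, and neither fits injection confined to the occiput. Label section 5.6 links weakened neck muscles to loss of breathing capacity in patients with respiratory disorders who depend on them, so the premise bears on an omitted item.

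**Step 4. Illustrate the scale.** Assume label rates applied to 65 subjects, the enrollment ceiling. Excess events = 65 × (Botox rate − placebo rate).

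- Neck pain: 65 × (0.0873 − 0.0275) = 3.9.
- Hospital-level migraine worsening: 65 × (0.01 − 0.003) = 0.46, about 0.5.

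The documents give no rates for this study's one-sided injection, so these are not forecasts.

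**The case against.** The best defense is that nothing is hidden. The full label and Medication Guide are in the file, and the Guide puts breathing problems first and lists headache and neck pain. That stands: the fault is a false claim of completeness in the narrative, and the attachment is what disproves it.

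A reader might infer that the boxed warning was left out altogether. It was not. Only breathing difficulty and distant spread as such are missing, and label section 5.2 reports no definitive serious distant-spread cases in chronic migraine at labeled doses. That bears on likelihood, not on whether the list is complete.

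A reader might also infer that unnamed events would go unreported. The documents do not show this. Subjects are asked to report any illness or discomfort and are warned of effects not yet known. Every serious adverse event goes to the IRB and the safety monitor within 24 hours, listed or not. Under-reporting of symptoms that resemble the underlying disease is plausible, but it is an assumption.

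The short list in the safety-methods part of the PHRC summary might be read as a further contradiction. It is worded as examples and claims no completeness.

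On scale, the label trials had two injection cycles at 155 to 195 Units, and this study has one planned one-sided session. Routine care would also include Botox, prior Botox treatment is expected, and intolerance is an exclusion. The illustrative events are therefore not all added by the study. The lower total dose does not settle the direction for neck events, however. The label's 155-Unit scheme gives 20/2 + 30/2 = 25 Units per side to paraspinal and trapezius muscles, against 30 or 40 on the injected side here.

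**Conclusion.** The completeness statement is wrong as written, in both section 5 and the PHRC summary. The lists omit the label's two most common chronic-migraine reactions, hospital-level migraine worsening and breathing difficulty. The site premise used to discount risk conflicts with both injection schemes. These findings rest on the text alone and need no assumption.

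The consequences are less certain. The excess of about 3.9 neck-pain events and 0.5 hospital-level worsenings depends on label rates carrying over to one unilateral session and on enrollment reaching 65. Actual rates may differ.

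It would go too far to conclude that subjects were not told of these risks, because the consent pages were not available for review. It would also go too far to say that the low-risk conclusion is wrong: it may survive a corrected list, but it has not been argued on one.

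Severity is minor to moderate. This is a correction to safety text and does not touch allocation, outcome, analysis or sample size.

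**What to change.** 1. Reconcile the lists in section 5 and the PHRC summary with the appended label: boxed warning, Table 15 and hospital-level migraine worsening.
2. Delete or correct the claim that all FDA-issued risks are listed.
3. Reconcile the statement about the injection site with sections 3.A and 10, and those two sections with each other. Which scheme applies is for the investigators.
4. Restate the risk conclusion on the corrected list.
5. Match the consent text if it copies the list.

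These changes need one amendment to the risk text.

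As a low-cost addition, ask about neck pain, migraine worsening, swallowing and breathing by name at contacts already planned. The textual contradiction does not require this. The reason for it is that the diary ends before injection and review relies on self-report. It costs a short checklist and possibly more minor events recorded. Clinical handling of any event stays with the investigators.

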6. RECRUITMENT AND CONSENT PROCEDURES

Recruitment

Patient screening, recruitment and consent will occur at [name] clinic (River Oaks Plastic Surgery Center) during a visit that determines their candidacy to undergo the surgery.

Patients are referred to the investigator or schedule an appointment independently for migraine surgery routinely. Subjects will be selected from among the patients that are referred to the investigator. A research nurse will initially explain participation in the study prior to the visit with the investigator. The patient will be given the consent forms and can take as much time as needed to consent for the study. The patient can also take the consent form home and call if interested. At the scheduled visit with the investigator he will reinforce that participation is voluntary and with their patients that participation is voluntary, that they do not have to participate, and the decision not to participate will not affect their care, now or in the future. The investigator can answer any questions the subject may have.

Subject Protection

Study subjects will not be employees of the study team.

